8.6 Sponsor and Clinical Research Organization's Responsibilities

The Sponsor is responsible for the ongoing safety evaluation of the investigational drugs being studied. The Sponsor and CRO are responsible for ensuring that expedited reports are made to all concerned investigators, to the IEC where required, and to all regulatory authorities of all adverse drug reactions that are both serious and unexpected, or findings that could adversely affect the health of patients, impact on the conduct of the trial, or alter the competent authority's authorization to continue the trial in accordance with local applicable regulations.

9 STATISTICAL METHODS AND DATA ANALYSES

9.1 General Principles

Data from Phase 1 will be summarized after approximately 80% of patients in Phase 1 have completed study treatment. Data will be presented by dose cohort and overall. At the end of Phase 2, any additional data collected for patients remaining on treatment after the Phase 1 data cut-off will be included in the final clinical study report.

For the Phase 1 escalation cohort, data will be reported based on all patient data up to the time when all patients have completed a minimum of 6 cycles of treatment or have discontinued the study. An updated analysis of DOR, PFS, and OS may be performed. Data will be presented by dose cohort and overall.

For the Phase 2 expansion cohort, the primary analysis of the study will be conducted after approximately 120 evaluable patients have been enrolled and treated/followed for at least 9 months. The primary analysis of Phase 2 will summarize data from the overall expansion cohort (approximately n=120 patients).

In order to explore whether results are consistent across prior therapy groups, key endpoints may be further summarized by prior therapy groups (for example: 1 systemic therapy and 1 LDT; 1-2 systemic therapies only; 1 LDT only, 1 checkpoint inhibitor and any LDT). Further details around the analysis plan, including any additional reporting of DOR, PFS, and OS with longer-term follow up that may be required will be defined in the Statistical Analysis Plan (SAP).

Data will be summarized using descriptive statistics. Categorical data will be presented as frequencies and percentages. For continuous data, mean, standard deviation, median, minimum, and maximum will be presented.

The following rules will be followed for reporting results unless stated otherwise:

- Screen failure patients are those who signed the informed consent, but never started the study treatment for any reason. For these patients, the eCRF data collected will not be included in analyses, but will be reported in the clinical study report as separate listings
- Baseline is defined as the last assessment prior to the first dose of treatment received (i.e., C1D1 pre-dose)
- Additional analyses not described here will be detailed in the SAP for the study

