	10%–29%) and immune responses (as assessed by area under the tumor response curves [AUC])
Study Design	
This is a Phase I12 study of IMCgp100 administered on a QW basis with an intra-patient escalation dosing regimen. The intra-patient escalation occurs at the third QW dose on C1D15. According to this regimen, all patients in the trial will receive 2 QW doses of IMCgp100 at a dose level below the identified RP2D-QW, and then a dose escalation will commence at the third QW dose at C1D15 with the goal to achieve a long-term dosing regimen at a dose higher than that identified for the RP2D-QW. In this dosing regimen, each patient will undergo a fixed intra-patient dose escalation (fixed dosing of 20 mcg at C1D1 and 30 mcg at C1D8), followed by the dose escalation beginning at C1D15. Patients will continue to receive the same escalated dose from C1D15 and thereafter. The dose escalation will identify the RP2D-IE.
 
The Phase 1 portion of the study will be a standard 3+3 dose escalation design. After the dose escalation portion is complete and the MTD or the RP2D-IE is identified, the Phase 2 expansion cohorts in mUM will be enrolled. These two cohorts will enroll patients with mUM and will enroll approximately 150 patients combined.
 
 • Cohort A will enroll patients with mUM in the second-line setting after disease progression following systemic treatment with a checkpoint inhibitor with any prior liver directed therapy (LDT) • Cohort B will enroll patients with mUM in the second or third-line setting with up to one prior LDT regimen • Additional details regarding expansion cohorts are outlined in Key Inclusion Criteria below, Section 3.2 and Section 5.2.

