2.2 Rationale for Study Design

[figure not shown]
IMCgp100-102 is a Phase 1/2 study of the QW intra-patient escalation dose regimen with IMCgp100 as a single agent in patients with mUM. The Phase 1 testing of this regimen will aim to achieve a higher exposure and C_{max} of IMCgp100 after doses at Cycle 1 Day 15 (C1D15) and thereafter than the exposures achievable at the RP2D of the fixed 50 mcg RP2D-QW without additional toxicity. Phase 1 testing will follow the standard 3+3 design with DLT as the endpoint and identification of the MTD and/or the RP2D for the Phase 2 intra-patient escalation regimen (RP2D-IE).

Once the appropriate dose for Phase 2 is identified (RP2D-IE), the Phase 2 expansion cohorts in UM will begin. Cohort A will recruit approximately 20 patients to further characterize the safety, tolerability, PK, and anti-tumor response of IMCgp100 in patients following therapy with a checkpoint inhibitor and any potential liver-directed therapy (LDT). Cohort B will recruit approximately 130 patients to further characterize the safety, tolerability, PK, and anti-tumor response of IMCgp100 in patients who have been previously treated with 1 or 2 prior lines of therapy in the metastatic or advanced setting, including chemotherapy, immunotherapy or targeted therapy and up to a single line of local, LDT. Prior checkpoint inhibitor is acceptable in Cohort B but is not required.

Additional details on Phase 2 Expansion cohorts are provided in [Section 3.2](#) and [Section 5.2](#).

These cohorts will provide homogenous populations in which to assess safety and anti-tumor efficacy with the goal to inform subsequent development of IMCgp100.

[figure not shown]

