PFS will be presented graphically using Kaplan Meier plots for all patients in the Phase 2 expansion cohorts. Median PFS time and the proportion of patients who are progression-free at 3, 6, 9, and 12 months will also be estimated. If there are a large number of patients achieving response (e.g., estimated ORR of 30%), the Kaplan-Meier plots for DOR will also be produced and the median DOR will be estimated. OS will be presented graphically using Kaplan Meier plots including all patients from the Phase 2 expansion. Median OS time and the proportion of patients who are alive at 3, 6, 9, and 12 months will be estimated.

The secondary endpoint to determine the rate and duration of MinR, defined as a reduction in the SLD of 10%–29% will be explored by: (1) summaries of the number (%) of MinR and associated durations; (2) summaries of the overall ORR + MinR and associated durations; and (3) waterfall plots of SLDs.

The secondary endpoint to determine the rate and duration of immune responses will be detailed in the SAP and be largely based on methods described by Gao et al. In summary, for each patient, the percentage change in the target lesion sum of longest diameters will be plotted over time and an AUC will be calculated over a fixed time-period (e.g., 9 months) post initial dose of IMCgp100. The AUC reflects both the depth and duration of tumor size reduction and may capture a delayed benefit of immunotherapy (Gao et al). Hepatic volume data will also be plotted and may be incorporated into the criteria for immune response.

Exploratory tumor assessments based on modified irRECIST will also be presented summarizing the best response by irRECIST and this will be compared with the best response from RECISTv.1.1.

The SAP will provide more detailed information on the data summaries for the Phase 1 dose escalation and the Phase 2 dose expansion.

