9.10.2 Phase 2 Dose Expansion Cohorts

The Phase 2 expansion cohorts of approximately 150 patients, including a minimum of 120 patients for RECIST evaluation, will provide a substantive dataset of safety, tolerability, and efficacy in uniform patient populations. Patients will be enrolled into 2 cohorts as described in [Section 3.2](#):

The primary analysis of the Phase 2 expansion will focus on the overall Phase 2 population. With 120 patients and an observed ORR of 10% or more, the precision around the estimation of ORR as assessed by 95% confidence intervals will be 5.3% to 16.8%. The study will also provide an adequate number of patients in which to assess the safety and tolerability of the RP2D-IE. For example, for AEs of interest, if 0 AEs are observed in a cohort of 120 patients, there will be 95% confidence that the true event rate is less than 3%. For 150 patients there will be 95% confidence that the true event rate is less than 2.4%.

In addition, the Phase 2 expansion data will provide an assessment of whether OS may exceed that achieved with currently available therapies, [REDACTED]

An IDMC will review safety data on an ongoing basis (approximately every 4 months) in conjunction with a review of safety data from the ongoing randomized study (IMCgp100-202). An interim review of both efficacy and safety data from the Phase 2 expansion will be performed by the IDMC after approximately 75 evaluable patients have been treated/followed for at least 6 months to enable an overall assessment of risk versus benefit.

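### Section 9.1 gives the Phase 2 primary-analysis cohort as about 120 where Section 9.10.2 implies up to about 150, and the interval 5.3–16.8% quoted for an ORR of 10% or above holds only at 12/120

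*Protocol*

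**What the plan says.** **Size of the cohort in the primary analysis.** Section 9.1 triggers the Phase 2 primary analysis once about 120 evaluable patients have been enrolled and treated or followed for at least 9 months. The next sentence describes what is analysed: "The primary analysis of Phase 2 will summarize data from the overall expansion cohort (approximately n=120 patients"). Section 9.10.2 states: "The primary analysis of the Phase 2 expansion will focus on the overall Phase 2 population". It sizes that population as follows: "The Phase 2 expansion cohorts of approximately 150 patients, including a minimum of 120 patients for RECIST evaluation".

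The synopsis agrees with the larger number: "These two cohorts will enroll patients with mUM and will enroll approximately 150 patients combined". Section 2.2 splits it as "Cohort A will recruit approximately 20 patients to further characterize the safety" and so on, plus about 130 in Cohort B. Sections 3.1 and 9.8 also give about 150.

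**Denominator.** Section 9.6.1 fixes the ORR denominator as FAS patients with measurable disease at baseline. Section 9.2.1 defines the FAS as assigned patients who received any full or partial dose. Criterion 8 in Section 5.2 requires measurable disease for Phase 2 entry.

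**Precision.** Section 9.10.2 reads "With 120 patients and an observed ORR of 10% or more, the precision around the estimation of ORR as assessed by 95% confidence intervals" and gives 5.3% to 16.8%. For safety it gives precision at both sizes, ending with "For 150 patients there will be 95% confidence that the true event rate is less than 2.4"%. For ORR it gives precision at 120 only.

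**The concern.** ORR by independent central review is the only Phase 2 primary endpoint, and the stated objective is to estimate it. An estimate needs one denominator, fixed before the data are seen. Here nearly the same words, the overall expansion cohort and the overall Phase 2 population, carry two sizes for the same analysis. A reader of 9.1 could conclude that the primary ORR is computed in about 120 evaluable patients. A reader of 9.6.1 and 9.10.2 would conclude that every dosed patient with measurable disease counts. The word evaluable does not settle it. The protocol explains it for dose-escalation decisions (6.3.4) and for safety (8.1), but not for tumour response in Phase 2.

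The precision sentence is a separate matter. It tells the reader what uncertainty to expect over a range of results, but the interval it quotes belongs to a single result in that range.

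**Working it through.** **1. Does any rule lead from 150 to 120?**

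- Start: about 150 enrolled in Phase 2 (20 + 130; Sections 2.2, 3.1 and 9.10.2).
- FAS (9.2.1): removes only patients never dosed. Section 7.1.1.1 classes a consented patient who does not start treatment as a screen failure.
- ORR denominator (9.6.1): removes only FAS patients without measurable disease at baseline, which 5.2 makes an entry requirement.
- Per-protocol set (9.2.3): the nearest thing to a response-evaluable set, but it is assigned to sensitivity analyses of secondary endpoints, not to the primary ORR.

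Reaching 120 from 150 means losing 30 patients, or 30/150 = 20%. None of these rules removes patients on that scale. The denominator is therefore up to about 150. It would be lower if accrual were incomplete at the cut or if some patients were found not to have measurable disease.

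**2. Reproducing the stated interval.** Section 9.8 names Clopper–Pearson for the interim ORR. For x responders in n patients, the two-sided 95% limits are

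- lower = 2.5th percentile of Beta(x, n − x + 1)
- upper = 97.5th percentile of Beta(x + 1, n − x)

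With x = 12 and n = 120 this gives 5.27% to 16.82%, which rounds to the protocol's 5.3% to 16.8%. Wilson (5.81–16.67%) and Wald (4.63–15.37%) do not reproduce it.

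**3. The same formula above 10%, and at n = 150.**

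| Responders / n | Observed ORR | 95% CI | Width (points) |
|---|---|---|---|
| 12/120 | 10.0% | 5.3–16.8% | 11.5 |
| 13/120 | 10.8% | 5.9–17.8% | 11.9 |
| 18/120 | 15.0% | 9.1–22.7% | 13.5 |
| 24/120 | 20.0% | 13.3–28.3% | 15.0 |
| 36/120 | 30.0% | 22.0–39.0% | 17.1 |
| 15/150 | 10.0% | 5.7–16.0% | 10.3 |

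One more responder than 12 already moves both limits. Above 10% the only part of the statement that stays true is that the lower limit is at least 5.3%. The upper limit exceeds 16.8%, and over the rates shown the interval widens.

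**4. Effect of the size question.** At 10% observed, going from 120 to 150 narrows the interval from 11.5 to 10.3 points.

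**The case against.** The best defence is that the protocol largely explains its two numbers. Section 9.10.2 places 120 inside 150 in one sentence, and the 9.1 sentence just before the disputed one speaks of 120 evaluable patients. The synopsis and Sections 2.2, 3.1 and 9.8 give enrolment or expansion size, not the number in the primary analysis. Overall in 9.1 may simply mean pooled across prior-therapy groups. This shows where 120 came from, and it disposes of one inference a reader might draw, that 120 and 150 are rival enrolment targets. It does not connect 120 to the 9.6.1 denominator, and 9.1 still uses 120 to describe the cohort analysed, not just the trigger.

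A second objection is that the denominator need not be the full 150. This stands. Section 9.6.1 does not say whether site or central readers judge measurability at baseline, and 9.1 does not say accrual will be complete at the cut. For that reason the figure here is up to about 150.

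On precision, the defence is that the arithmetic is right and the sentence is a planning illustration, since the reported interval will come from the data. That also stands. A reader might infer a miscalculated sample size, but the documents do not support this: 12/120 reproduces the figure exactly. Nor is 30% a planning value. Section 9.6.1 uses it only as an example of when to draw duration-of-response plots: "If there are a large number of patients achieving response (e.g., estimated ORR of 30"%). The 30% row shows how far the sentence is stretched, not a result the design expected.

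**Conclusion.** Both statements are wrong as written, and both are minor. Section 9.1 sizes the primary-analysis cohort at about 120, while 9.10.2 and the denominator rules imply all dosed Phase 2 patients with measurable disease, up to about 150. The interval in 9.10.2 is correct at 12/120 and at no higher rate. The aim is estimation, so no hypothesis test or success threshold rests on either. The size question is worth about 1.3 points of interval width at an observed 10%.

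A reader might go further and infer that patients beyond the 120 will have too little follow-up and pull the ORR down. The documents do not support this as a finding. They give no accrual rate, and 9.1 leaves further analysis detail to the SAP. The effect is also small. Assume a true ORR of 10%, a 39-week wait after the 120th enrolled patient, and 12 weeks as the earliest scheduled confirmed response (week-8 scan plus 4 weeks). The fall is then 0 points at 1.5 patients per week or faster and 0.2 at 1 per week. It is 0.6 at 0.75 per week (9 of 149 patients too early: 10% × 140/149 = 9.4%) and 0.4 at 0.5 per week. These rates are assumptions, and no minimum follow-up rule is proposed here.

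**What to change.** **Section 9.1.** State that the Phase 2 primary analysis summarises all Phase 2 FAS patients, with the ORR denominator as in 9.6.1 (up to approximately 150), and that approximately 120 evaluable patients followed for at least 9 months sets the timing only. Define evaluable for this trigger. If the sponsor instead intends the primary ORR to use only the 120 or so evaluable patients, change 9.6.1 and 9.10.2 to say so.

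**Section 9.10.2.** Delete the words 'or more' and write: 10% observed: 95% CI 5.3–16.8% at n=120, 5.7–16.0% at n=150.

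**Cost.** Text changes in two sections, or in 9.6.1 and 9.10.2 if the sponsor takes the alternative. No extra patients, data or delay to the cut.

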9.2 Analysis Sets

9.2.1 Full Analysis Set

The Full Analysis Set (FAS) comprises all patients assigned to treatment, who received at least 1 full or partial dose of IMCgp100. The FAS will be used for all demography, baseline characteristics, and efficacy data summaries and analyses.

9.2.2 Safety Analysis Set

The Safety Set includes all patients who have received at least 1 full or partial dose of IMCgp100. Patients will be classified in this set according to initial treatment received. The safety set will be used for the safety summary of the study.

9.2.3 Per-protocol Analysis Set

The Per Protocol Set (PPS) consists of a subset of FAS patients who meet these 4 criteria: (1) presence of measurable disease, (2) 1 post-baseline tumor assessment or discontinue prior to the first tumor assessment, (3) received at least 1 dose of treatment and, (4) no violation of key inclusion or exclusion criteria.

Patients in the PPS will be classified according to planned treatment. The PPS will define the patients used in the sensitivity analysis of the secondary endpoints. If the PPS and the FAS are identical, then analyses described by the PPS below will not be performed.

9.3 Patient Demographics and Other Baseline Characteristics

Demographic data, baseline disease characteristics and other baseline data will be listed in detail. Qualitative data (e.g., performance status) and quantitative data (e.g., weight) will be summarized by descriptive statistics.

9.4 Treatment Data

Actual dose and duration in days of treatment for IMCgp100, as well as, the dose intensity (actual dose received/actual duration) and relative dose intensity (the ratio of dose intensity to planned dose/planned duration) will be summarized by descriptive statistics by treatment group.

Concomitant medications and significant non-drug therapies prior to and after the start of the study treatment will be listed by patient and summarized by Anatomical Therapeutic Chemical term and treatment group.

The reason for discontinuation from treatment will be summarized and listed, along with dates of first and last doses, duration of exposure to each study drug, and date of discontinuation for each patient.

9.5 Primary Analysis

9.5.1 Variables

The primary variable in the Phase 1 dose escalation phase of the study is the incidence of DLT.

The primary variable in the Phase 2 dose expansion phase of the study is ORR by RECISTv.1.1 assessed by ICR.

9.6 Secondary Analyses

9.6.1 Efficacy

Analysis of efficacy endpoints will be performed using the FAS unless otherwise noted.

For the Phase 1 escalation cohorts, tumor-based endpoints will be assessed using local investigator assessment and ICR where available for both RECISTv.1.1 and modified irRECIST. For the Phase 2 expansion cohorts, tumor-based endpoints will be assessed using ICR data for both RECIST v1.1 and modified irRECIST. ORR and other RECIST-based endpoints as assessed by the local radiologist will be summarized as a sensitivity analysis.

ORR is defined as the proportion of patients with measurable disease with at least 1 visit response of CR or PR that is confirmed at least 4 weeks later, as defined in RECIST v.1.1.

The denominator in the calculation of the ORR will be the number of patients in the FAS with measurable disease at baseline. Data obtained up until progression, or last evaluable assessment in the absence of progression, will be included in the assessment of ORR. However, any CR or PR, which occurred after further anti-cancer therapy was received, will not be included in the numerator of the ORR calculation. Disease control rate is defined as the proportion of patients with a best overall response of CR or PR or SD recorded at least 24 weeks (\pm 1 week) after commencement of study drug and prior to any PD event.

For all efficacy parameters, data will be listed, summarized, or analyzed by treatment group (dose cohort) for the Phase 1 dose escalation and overall for the Phase 2 expansion cohorts.

In order to explore whether the Phase 2 efficacy results are consistent across prior therapy groups, key endpoints (including ORR and DoR) may be further summarized by prior therapy groups (for example: 1 systemic therapy and 1 LDT; 1-2 systemic therapies only; 1 LDT only, 1 checkpoint inhibitor and any LDT).

Further subset analyses of efficacy by LDH (above or below institutional ULN) and hepatic metastases (present or absent) may be performed if an adequate number of patients with and without the prognostic factor are available for analysis (Valpione, 2015).

ORR and DCR will be summarized with accompanying 95% confidence intervals.

PFS, along with DOR and time to response for patients who experience a CR or PR at any time on study will be listed by patient.

[figure not shown]
PFS will be presented graphically using Kaplan Meier plots for all patients in the Phase 2 expansion cohorts. Median PFS time and the proportion of patients who are progression-free at 3, 6, 9, and 12 months will also be estimated. If there are a large number of patients achieving response (e.g., estimated ORR of 30%), the Kaplan-Meier plots for DOR will also be produced and the median DOR will be estimated. OS will be presented graphically using Kaplan Meier plots including all patients from the Phase 2 expansion. Median OS time and the proportion of patients who are alive at 3, 6, 9, and 12 months will be estimated.

The secondary endpoint to determine the rate and duration of MinR, defined as a reduction in the SLD of 10%–29% will be explored by: (1) summaries of the number (%) of MinR and associated durations; (2) summaries of the overall ORR + MinR and associated durations; and (3) waterfall plots of SLDs.

The secondary endpoint to determine the rate and duration of immune responses will be detailed in the SAP and be largely based on methods described by Gao et al. In summary, for each patient, the percentage change in the target lesion sum of longest diameters will be plotted over time and an AUC will be calculated over a fixed time-period (e.g., 9 months) post initial dose of IMCgp100. The AUC reflects both the depth and duration of tumor size reduction and may capture a delayed benefit of immunotherapy (Gao et al). Hepatic volume data will also be plotted and may be incorporated into the criteria for immune response.

Exploratory tumor assessments based on modified irRECIST will also be presented summarizing the best response by irRECIST and this will be compared with the best response from RECISTv.1.1.

The SAP will provide more detailed information on the data summaries for the Phase 1 dose escalation and the Phase 2 dose expansion.

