4. Modification of Section 11.3 to harmonize the informed consent procedures with inclusion criterion #2 and clarify the informed consent process.

Amendment 6

Amendment Rationale

This amendment transitions the dose expansion cohort component of the study, designed to explore the recommended Phase 2 dose that was defined in the Phase 1 testing of the intra-patient escalation regimen (RP2D-IE, 68 mcg) to more formal Phase 2 testing in patients with metastatic uveal melanoma who are treated in the second or third line setting in this trial (Amendment 6, Protocol version 7.0, 15 December 2017).

Tumor responses have been observed in the preliminary dose escalation cohorts of this study and these responses have been associated with long duration of response as reported recently ([Sato, 2017](#); [Carvajal, 2017](#)). Based on the observation of durable partial responses and minor responses (defined as a tumor response where the sum of the longest diameters [SLD] of target lesions is reduced by 10%–to 29%) in the dose escalation cohorts of this study, the dose expansion cohort in the trial is modified to provide a formal analysis of the anti-tumor efficacy in this patient population using the objective response rate (ORR) by independent review as the primary efficacy endpoint in this portion of the study. Two separate expansion cohorts in this study are defined based on prior therapy:

1. Cohort A: Patients will have experienced disease progression with 1 systemic treatment regimen containing a checkpoint inhibitor, including either a CTLA4 inhibitor (ipilimumab or tremelimumab) and/or a PD-1/PD-L1 inhibitor. Any prior liver-directed therapy (LDT) is acceptable in this cohort.
2. Cohort B: Patients will have experienced disease progression with 1 or 2 prior lines of therapy, including up to 1 prior line of LDT. LDT will be considered a line of therapy for enrolling this cohort. Prior checkpoint inhibitor therapy is acceptable but not required in this cohort.

Given the formal efficacy measures implemented in this dose expansion cohort, the study will be designated as a Phase 1/2 to reflect this new endpoint.

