9.8 Interim Analysis

For the Phase 1 cohorts, the dose-escalation design foresees that decisions based on the current data are taken before the end of the study. More precisely, after each cohort in the dose escalation part, the next dose will be chosen depending on the observed data (based on safety, tolerability, PK, pharmacodynamic, and efficacy data, and recommendations from participating investigators). Details of this procedure and the process for communication with investigators are provided in [Section 6.3.3](#).

For the Phase 2 expansion (approximately n=150), an IDMC will review the safety data on an ongoing basis. In addition, a benefit-risk assessment involving review of efficacy and safety data will take place once approximately 75 evaluable patients have been treated/followed for at least six months. The primary endpoint of ORR, as assessed by the ICR, will be summarised with 95% confidence intervals (Clopper Pearson method). ORR based on the local radiological assessment will be summarised as a sensitivity analysis. Duration of response and other secondary efficacy endpoints will be described. Further details will be provided in the SAP.

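### Protocol Section 9.6.1 makes the Kaplan-Meier curve and median for duration of response depend on an undefined large responder count, while PFS and OS get theirs unconditionally

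*Protocol*

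**What the plan says.** Protocol Section 4.5 lists DOR as a secondary endpoint beside PFS. Section 9.6.1 then treats the time-to-event endpoints differently:

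- **PFS:** a Kaplan-Meier plot for all Phase 2 patients, and "Median PFS time and the proportion of patients who are progression-free at 3, 6, 9, and 12 months will also be estimated". No condition.
- **OS:** "OS will be presented graphically using Kaplan Meier plots including all patients from the Phase 2 expansion", with the median and the same four fixed-time proportions. No condition.
- **DOR:** "If there are a large number of patients achieving response (e.g., estimated ORR of 30%), the Kaplan-Meier plots for DOR will also be produced"; the median DOR is covered by the same conditional sentence.

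The other DOR outputs in the protocol are:

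- DOR and time to response "for patients who experience a CR or PR at any time on study will be listed by patient" (Section 9.6.1);
- optional summaries by prior-therapy group, and durations tabulated with the minor-response and combined-response summaries (Section 9.6.1);
- at the interim review, "Duration of response and other secondary efficacy endpoints will be described" (Section 9.8);
- possible further reporting with longer follow-up, left to the SAP (Section 9.1).

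None of these commits to an estimate that allows for responses still ongoing at the data cut-off. The primary analysis is timed for when about 120 evaluable patients "have been enrolled and treated/followed for at least 9 months" (Section 9.1). Section 9.10.2 illustrates the precision of the ORR by "With 120 patients and an observed ORR of 10% or more", giving a 95% interval of 5.3% to 16.8%.

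**The concern.** The primary endpoint is a response rate in a single-arm expansion, and such a rate is hard to interpret without knowing how long the responses last. The minimum follow-up is 9 months, and the Amendment 6 rationale says of the dose-escalation responses that "these responses have been associated with long duration of response as reported recently". Many responses could therefore be ongoing at the cut-off, so that their observed durations are only lower bounds.

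The condition has three weaknesses:

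1. It has no threshold. Whether the estimate is produced would be decided after the response data have been seen.
2. Its only example, an ORR of 30%, is three times the rate in the protocol's own precision statement and lies above the upper limit of that interval.
3. It switches on the wrong quantity. The number of responders determines how precise a DOR estimate is. It does not determine the share of responses that are censored, which is the reason a Kaplan-Meier estimate is needed.

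**Working it through.** **1. The protocol's own figure.** An ORR of 10% in 120 patients is 12 responders. The Clopper-Pearson 95% limits for 12/120 are the 0.025 quantile of Beta(12, 109) and the 0.975 quantile of Beta(13, 108), that is 5.27% and 16.82%. This reproduces the stated 5.3% to 16.8%.

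**2. Chance of meeting the condition if 30% is the cut-off.** The trigger is 0.30 × 120 = 36 responders, against 12 in the precision case. With X ~ Binomial(120, p):

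| True ORR p | P(X ≥ 36) |
|---|---|
| 10% | 1.0 × 10⁻⁹ |
| 15% | 2.3 × 10⁻⁵ |
| 16.8% | 2.5 × 10⁻⁴ |
| 20% | 0.6% |
| 25% | 12% |
| 30% | 53% |

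**3. Sensitivity to the undefined cut-off.** The 30% is only an example, so lower readings are possible:

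| Cut-off (responders of 120) | p = 10% | p = 16.8% | p = 20% |
|---|---|---|---|
| 20 | 1.6% | 55% | 85% |
| 24 | 0.08% | 20% | 54% |
| 36 | 1.0 × 10⁻⁹ | 0.02% | 0.6% |

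The answer moves by orders of magnitude with the meaning given to the undefined word.

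**4. Does the responder count matter for censoring?** Illustrative simulation, 4,000 replicates per cell. The assumptions are mine, not the protocol's: exponential DOR; follow-up from first dose uniform between 9 and 21 months; first response at week 8, 16 or 24 with equal probability. DOR is censored at follow-up minus time to response. The true proportion still in response at 6 months is 0.5^(6/median).

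| True median DOR (months) | 6 | 9 | 12 | 18 |
|---|---|---|---|---|
| Responses censored (12 or 36 responders, within 1 point) | 30% | 44% | 53% | 65% |
| KM median not reached, 12 responders | 2% | 14% | 31% | 59% |
| KM median not reached, 36 responders | 0% | 2% | 18% | 59% |
| True proportion in response at 6 months | 0.50 | 0.63 | 0.71 | 0.79 |
| Mean KM estimate at 6 months, 12 responders | 0.50 | 0.63 | 0.71 | 0.79 |
| SD of that estimate, 12 responders | 0.147 | 0.142 | 0.132 | 0.116 |
| SD of that estimate, 36 responders | 0.085 | 0.082 | 0.077 | 0.068 |

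The censored share does not depend on the number of responders. With 12 responders the Kaplan-Meier proportion is on target but imprecise: at a true median of 12 months the half-width is 1.96 × 0.132 = 0.26.

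**5. What a summary that ignores censoring would show.** In the same simulation the plain median of observed durations averaged about 7.9 months when the true median was 12, and 8.9 months when it was 18. The shortfall was the same with 12 and with 36 responders.

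**The case against.** The best case for the text is that it sets a minimum, not a prohibition. It promises the curve when responders are many and does not say it will be withheld otherwise. Sections 9.1 and 9.6.1 send further detail to the SAP, which was not available here, and which outputs accompany a secondary endpoint is ordinary SAP content. PFS and OS use every Phase 2 patient while DOR uses responders only, so a size condition can be read as a normal precision judgement; Section 9.6.1 applies a similar one to subset analyses. With about 12 responders, a listing that marked ongoing responses would let a reader rebuild the curve. Finally, the very small probability at a 10% ORR depends on taking an example as a cut-off and an illustration as a forecast.

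Parts of this stand. The 1 in a billion figure is not the effect of the rule; it applies only if 30% is the threshold and 10% the true rate, and Section 9.10.2 allows for more than 10%. The SAP may already contain an unconditional analysis. The gain with few responders is modest: when responses are long, the median is often not reached even with 36 responders.

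It does not remove the point. The condition is a rule the protocol writes, not a detail it leaves open, so an unconditional SAP analysis would still have to be reconciled with it. The protocol does not say that the listing will flag ongoing responses. Low precision is a reason to show a confidence interval or report the median as not reached, not to omit the estimate.

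**Conclusion.** The concern holds, as a cheap improvement. As written, the protocol guarantees no censoring-adjusted summary of DOR unless responders are numerous in a sense it does not define, and its one example is three times the ORR in its own precision statement. At that 10% rate, about 12 of 120 patients would respond and the 30% example would practically never be met. The primary ORR analysis and the sample size are unaffected; what is at stake is the interpretation of the ORR.

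The binomial figures are exact but rest on reading 30% as the cut-off. The censoring shares of 30% to 65% rest on the assumed exponential durations, follow-up spread and response times, and are illustrative. That the share of censored responses does not depend on the number of responders follows whenever durations and follow-up are distributed alike in both cases. The expectation that many responses will be ongoing rests on the 9-month minimum and the sponsor's own description of the dose-escalation responses.

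**What to change.** Delete the conditional clause in Section 9.6.1 and replace it with a commitment such as:

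> *Kaplan-Meier plots of DOR will be produced for all Phase 2 patients with a CR or PR confirmed by independent central review, whatever their number. The numbers of events and censored responses, the median with 95% CI (or not reached), and the proportions still in response at fixed times supported by follow-up (for example 3, 6 and 9 months) will be reported alongside the by-patient listing.*

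Removing the condition while keeping the curve and median is the essential part. The interval, counts and fixed times could instead go in the SAP, provided the two documents agree.

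The cost is one sentence, one table and one figure, with no extra patients or data. The drawback is a wide interval if responders are few: about ±26 percentage points on the 6-month proportion with 12 responders and a true median of 12 months, and possibly a median that is not reached.
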